6.4 Study intervention compliance

When participants self-administer study intervention(s) at home, compliance with study intervention will be assessed at each visit. Compliance will be assessed by direct questioning and counting returned tablets during the site visits and documented in the source documents and eCRF. Deviation(s) from the prescribed dosage regimen should be recorded. Unopened and undamaged bottles of returned study intervention may be re-dispensed to the same participant.

A record of the quantity of tablets dispensed to and administered by each participant must be maintained and reconciled with study intervention and compliance records. Intervention start and stop dates, including dates for intervention delays and/or dose reductions will also be recorded.

A system to remind the participants of study intervention self-administration and to document the intake may be used. Such a system may consist of a mobile application and web portal components. Study drug intake may be documented by the participants by scanning a barcode with a mobile phone using a dedicated smartphone application. These scans are recorded via a web-portal. An alternative methodology, e.g. a paper based diary, may be used for documenting study intervention intake. If study intervention intake has not yet been documented, the participants may be reminded to take the study intervention, e.g. by telephone, email, push-notification, text message, at defined time points prior and after the scheduled time of study intervention intake.

IWRS will be used for drug accountability on a patient basis. Drug returns, reconciliation and destruction information will be captured in the IWRS.

On all visit days during the treatment period, plasma samples will be taken to determine the concentrations of the study intervention.

Taken together, these measures are deemed appropriate to support participants adherence and to detect participants that are systematically non-adherent.

09 FEB 2023 Page: 41 of 95

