#### Intercurrent events:

- Dropout due to a VTC in the study eye: *composite variable strategy* (analyze study participant as non-responder)
- Dropout ...

... before Visit 9 (week 12) composite variable strategy (analyze study participant as non-responder)

... after Visit 9 (week 12) with EoT DRSS assessment performed within 4 weeks of treatment discontinuation

while on treatment strategy (use the last available DRSS assessment (LOCF)

... after Visit 9 (week 12) with EoT DRSS assessment performed more than 4 weeks after treatment discontinuation

*while on treatment strategy* (use the last available DRSS assessment prior to treatment discontinuation (LOCF))

• Non-compliance with study intervention, defined as actual drug intake lower than 80% or higher than 120% of the planned drug intake per protocol: *principal stratum strategy* (exclusion from analysis, as an adequate imputation of response information is considered not possible)

The secondary estimand (analysis on FAS) is identical to the primary estimand (analysis on PPS) with the exception that the condition relating to compliance is not included.

Version 3.0

The other estimand (analysis on PPS) is defined below:

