## 4.2.2 Main Analytical Approach

For the primary analysis, the last observation before missing DRSS values will be carried forward (LOCF) to impute missing values if the participant dropped out after visit 9 (week 12) and the EoT DRSS assessment was performed within 4 weeks of treatment discontinuation (*while on treatment strategy*). If the last measured DRSS score already showed an improvement by  $\geq 2$  steps at the last measurement prior to the missing assessment, the participant will be considered a responder for the primary endpoint. Otherwise, the participant will be considered a non-responder. If the participant dropped out after visit 9 (week 12) and the EoT DRSS assessment was performed more than 4 weeks after treatment discontinuation the last available DRSS assessment prior to treatment discontinuation will be used (LOCF) (*while on treatment strategy*). Participants who dropped out before visit 9 (week 12), or who had a VTC in the study eye prior to the missing assessment will be considered non-responders regardless of the DRSS level (*composite variable strategy*).

Treatment groups will be runcaciguat and placebo, actually administered dose levels will not be considered for this analysis.

Primary efficacy analyses will be performed on the PPS and will include only study intervention compliant participants (*principal stratum strategy*). In addition, sensitivity analyses will be performed on the FAS. Further analyses may include a separate analysis for each runcaciguat maintenance dose level that was reached during titration (on the PPS). Participants will be analyzed according to the treatment (i.e., runcaciguat or placebo) they actually received.

The study will be analyzed using Bayesian inference with non-informative priors. PoC shall be defined as fulfillment of the following criteria:

•  $P(\pi_{ACT} - \pi_{PLC} > 0 | data) \ge 0.9$ i.e., the posterior probability that the difference between  $\pi_{ACT}$  and  $\pi_{PLC}$  is greater than 0 (clinical activity) given the data observed in the study needs to be 90% or more,

and

•  $P(\pi_{ACT} > 0.25 | data) \ge 0.5$ i.e., the posterior probability that  $\pi_{ACT}$  is greater than 0.25 (clinical relevance) given the data observed in the study needs to be 50% or more.

95% credible intervals will also be presented for  $\pi_{ACT}$  and for  $\pi_{PLC}$ 

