#### 4.5.1 Treatment Compliance, Duration and Exposure

Tables will be presented for the FAS and PPS.

Frequency tables and summary statistics will be presented for total dose, treatment dose per week, and treatment duration (absolute duration and frequencies with weekly intervals). In addition, treatment compliance will be summarized presenting the percent of tablets that were actually taken out of the planned number of tablets. Frequencies of participants showing compliance <80%, 80-120%, and >120% of the planned tablets will be presented.

The frequencies of dose modifications will be presented by treatment group and visit, especially to assess the escalation, maintenance, reduction, and withdrawal of doses, including the reasons for maintenance, reduction, or withdrawal. Furthermore, the frequency of participants being treated on a certain dose level will be presented by treatment group, visit and dose level to assess the titration level being reached during up-titration and in the maintenance phase.

A listing with the actual dose levels or sham-titration levels for each visit will be presented to get an overview of the individual titration schemes.

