### 5. Sample Size Determination

For the evaluation, a Bayesian concept for inference will be used, which is based on the posterior probabilities that the research hypotheses are true. Clinically relevant benefit of runcaciguat in treatment of advanced NPDR will be considered established and will result in "PoC" if the following criteria are met:

- $\geq$  90% posterior probability for the hypothesis of clinical activity (i.e.,  $P(\pi_{ACT} > \pi_{PLC} | data) \geq 0.9$ )
- $\geq 50\%$  posterior probability for the hypothesis of clinical relevance (i.e.,  $P(\pi_{ACT} > 0.25 | data) \geq 0.5$ ).

The sample size has been chosen to provide at least 90% probability to obtain PoC under the following assumptions:

- True response probability for placebo: 10%
- True response probability for runcaciguat 120 mg: 35%

The response criterion is assumed to be binomially distributed. For the Bayesian evaluation, a Jeffries' prior (i.e., a Beta (0.5;0.5)-prior) has been used. Sample size was determined with a simulation approach using the R environment.

CONFIDENTIAL	Statistical Analysis Plan BAY 1101042 / 20739	
	Version 3.0	Page: 32 of 35

To be able to declare both clinical activity and clinical relevance  $\geq 40$  evaluable participants are needed in both groups.

98 participants will be randomly assigned to the study intervention such that approximately 80 evaluable participants complete the study. Of 98 participants, 18 participants will be randomized with a ratio of 2:1 to highest runcaciguat dose and placebo for Part 1. 80 participants will be randomized with a ratio of 1:1 to placebo and runcaciguat for Part 2 (Table 5-1).

Table 5-1: Planned sample size

	Target dose	Part 1	Part 2	Total
Randomized	Placebo	6	40	46
	30 mg	-	-	-
	60 mg	-	-	-
	90 mg	-	-	-
	120 mg	12	40	52
	Overall	18	80	98
Evaluable*				80

\*Minimum evaluable for primary endpoint.

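### Does the 80% compliance exclusion cancel the SAP's own rules for dropouts in the per-protocol analysis that decides proof of concept?

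*SAP*

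**What the plan says.** SAP 1.1 lists the intercurrent events of the primary estimand, which is analysed on the per-protocol set (PPS). A dropout "before Visit 9 (week 12) composite variable strategy (analyze study participant as non-responder") stays in the analysis. A dropout after Week 12 is scored by LOCF, and a dropout due to a vision-threatening complication (VTC) in the study eye counts as a non-responder. The last item on the list is "Non-compliance with study intervention, defined as actual drug intake lower than 80% or higher than 120% of the planned drug intake per protocol". These participants are left out, "as an adequate imputation of response information is considered not possible". SAP 4.2.2 repeats that the primary analysis "will include only study intervention compliant participants".

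The secondary estimand, on the FAS, is the same "with the exception that the condition relating to compliance is not included". SAP 4.5.1 describes compliance as "the percent of tablets that were actually taken out of the planned number of tablets", again without a period. Protocol 6.4 says how it is measured: "Compliance will be assessed by direct questioning and counting returned tablets during the site visits". SAP 3 leaves the detailed validity definitions to the ACIR document, which is not among the documents reviewed.

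**The concern.** Two rules reach the same participants in the same analysis. One keeps an early dropout as a non-responder; the other removes anyone whose intake is too low. If planned intake is the full 48-week course, everyone who stops early is also non-compliant and is removed before the dropout rule can act. The primary analysis would then approach a completers' analysis, and the multiple-imputation analysis of SAP 4.2.3, which carries the same exclusion, would have few participants left to impute.

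This could affect the decision, because proof of concept (PoC) is judged on the PPS. Removing early non-responders raises the runcaciguat rate; removing later LOCF responders lowers it. Two passages seem to leave the 48-week reading open: SAP 1.2 plans 48 weeks of treatment for each participant, and SAP 5 says that "98 participants will be randomly assigned to the study intervention such that approximately 80 evaluable participants complete the study".

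**Working it through.** **Inputs.** 15 mg tablets and weekly steps of 30, 60, 90 and 120 mg, i.e. 2, 4, 6 and 8 tablets a day (Protocol 6.1.1 and 6.5.1); 48 weeks of treatment; 52 runcaciguat and 46 placebo participants randomised, true response 35% v 10%, Beta(0.5, 0.5) prior (SAP 5). PoC needs P(π_ACT > π_PLC) ≥ 0.9 and P(π_ACT > 0.25) ≥ 0.5.

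**The plan's own figure.** Exact enumeration with 40 evaluable per arm gives P(PoC) = 90.3%, in agreement with the stated minimum of 90%.

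**Step 1: what a 48-week denominator would do.** At full titration, planned tablets are 7 × (2 + 4 + 6 + 45 × 8) = 2604. With perfect adherence:

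| Maintenance dose | 48-week total | Share by end of Week 12 | Week 38 | Week 39 |
|---|---|---|---|---|
| 120 mg | 2604 | 588/2604 = 22.6% | 78.5% | 80.6% |
| 90 mg | 1974 | 23.4% | 78.7% | 80.9% |
| 60 mg | 1330 | 24.2% | 78.9% | 81.1% |
| 30 mg | 672 | 25.0% | 79.2% | 81.25% |

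On this count the pre-Week-12 rule never acts, and the LOCF and VTC rules act only for stops in about the last nine weeks.

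**Step 2: which reading the text supports.**
- The same list in SAP 1.1 gives dropouts their own scoring rules. It excludes non-compliers because their response cannot be imputed. That reason does not fit dropouts, whose response the list has just supplied. A 48-week denominator would empty the rules beside it.
- The Version History says that the estimands were added to use the data of early discontinuers. SAP 4.2.3 imputes their response.
- SAP 1.2 also says that treatment lasts 48 weeks if tolerated, or until a VTC or PDR develops. Protocol 7.1.1 lists cases in which treatment must stop, and Protocol 7.1.3 bars restarting after a permanent stop. No intake is planned after that point.
- SAP Appendix 1 (6.1) defines study completers by the Week 48 visit, whether or not treatment stopped. The SAP 5 sentence about evaluable completers is therefore not a statement about tablets.

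**Step 3: dose basis.** A fully adherent completer held at 90 mg takes 1974/2604 = 75.8% of the full-titration count; at 60 mg it is 1330/2604 = 51.1%. If planned meant the 120 mg target, these participants would leave the PPS. Yet SAP 4.2.2 foresees PPS analyses by maintenance dose level, and Protocol 6.5.1 itself directs that doses be held or reduced. Planned intake under the protocol is thus intake at the assigned dose.

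**Step 4: size if the 48-week reading were used.** Early dropouts are removed on one reading and counted as non-responders on the other. The dropout counts are assumptions, since the documents give neither timing nor rates by arm.

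| Early dropouts, active/placebo (none later) | P(PoC), 48-week | P(PoC), to discontinuation | Decisions differ |
|---|---|---|---|
| 1/1 | 0.925 | 0.925 | 0.0% |
| 2/2 | 0.914 | 0.914 | 0.0% |
| 3/2 | 0.901 | 0.899 | 0.2% |
| 4/3 | 0.924 | 0.885 | 3.9% |
| 8/4 | 0.912 | 0.795 | 11.7% |

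The jump between 3/2 and 4/3 is a step in the relevance criterion: at least 12 responders are needed for n = 45 to 48 and 13 for n = 49 to 52. With 12 responders, P(π > 0.25) is 0.511 at 12/48 (met) and 0.384 at 12/52 (not met).

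With later dropouts added (3/2 early plus 3/2 later), decisions differ in 3.3% of trials if the later ones respond like completers, 5.8% if none respond, and 3.4% if half of the active ones do. For 4/3 plus 4/3 the figures are 5.0%, 11.3% and 4.1%. When later dropouts can respond, the disagreements run in both directions.

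**The case for a change.** The strongest case for a change is that the SAP itself sets the 80% and 120% limits, so it should be readable without another document. The denominator decides who enters the analysis on which PoC rests. If the intent is plain, two sentences would record it; if they are missing, whoever programs the derivation makes the choice. The FAS analysis would show a divergence but does not decide PoC. Nor is the support in SAP 1.2 complete: Protocol 7.1.1 makes withdrawal after a VTC optional, so a VTC does not always end planned treatment.

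Some of this stands. The period and dose basis are not written in SAP 1.1, 4.2.2 or 4.5.1, and a line stating them, or pointing to the ACIR document, would be tidy. What does not stand is that the two readings are equally open. The 48-week reading makes several rules in one list nearly void and defeats the stated purpose of introducing estimands. The larger disagreement rates also need unfavourable assumptions: 11.7% takes 12 dropouts before Week 12, out of the 98 − 80 = 18 non-evaluable participants the plan allows for, and 11.3% takes 14 dropouts with no response among the later ones.

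**Conclusion.** No change to the plan is needed. A detail is missing, and the surrounding text fills it: compliance is tablets taken over tablets prescribed at the assigned dose, up to permanent discontinuation. The dropout rules then act as listed, and the exclusion reaches only participants who took too little or too much while on treatment, including any who later dropped out. An analyst who applies the rules as written gets a sound result.

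If the less natural reading were used, the effect on PoC would be 0.0% to 0.2% of trials with one to three early runcaciguat dropouts and none later, and 3.3% to 11.7% in the heavier dropout patterns examined. All these figures assume 35% v 10% response, 52 and 46 randomised, and no on-treatment non-compliers. A divergence would be visible in the FAS analysis, which has no compliance condition, in the compliance tables for both sets (SAP 4.5.1), and in the reported reasons for restricted validity (SAP Appendix 1). The conclusion rests on the SAP and protocol alone; the ACIR document could confirm it but was not available.

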#### Primary Objective: See above.

#### Estimand label: other

#### **Endpoint:**

DRSS improvement  $\geq 2$  steps at 48 weeks of treatment in the study eye

#### **Population:**

Adult patients with

- moderately severe to severe NPDR in the study eye (DRSS levels 47 or 53)
- Diabetes type 1 or 2
- BCVA ETDRS letter score in the study eye of ≥ 69 letters (approximate Snellen equivalent of 20/40 or better)
- Refraction with a spherical equivalent from -6 dpt to +5 dpt

#### **Treatment condition:**

Runcaciguat vs. placebo

#### **Population level summary:**

The estimated difference in the proportion of responders between interventions.

#### **Intercurrent events:**

- Dropout due to a VTC in the study eye: *composite variable strategy* (analyze study participant as non-responder)
- Missing DRSS assessment on Visit 15 (week 48) due to early discontinuation: *hypothetical strategy* (multiple imputations will be performed for the responder criterium)
- Non-compliance with study intervention, defined as actual drug intake lower than 80% or higher than 120% of the planned drug intake per protocol: *principal stratum strategy* (exclusion from analysis, as an adequate imputation of response information is considered not possible)

#### 1.2 Study Design

This is a randomized, double-masked parallel study with two study arms enrolling N=98 patients with NPDR. The study is conducted as a placebo-controlled study. Total treatment duration is 48 weeks. The primary endpoint will be the number of participants with  $a \ge 2$ -step improvement (reduction) in the DRSS after 48 weeks of treatment in the study eye.

A steering committee consisting of ophthalmologists and diabetologists (masked) is put in place to provide scientific and operational recommendations to the study protocol and may be consulted to support decisions in study conduct. An independent DMC is set up to provide recommendations based on unmasked review of data, if needed (see section 4.7.1).

This Phase 2 study is conducted to determine whether runcaciguat, administered at once daily oral doses of a modified-release formulation, is more effective in treating NPDR than placebo. The study is subdivided into two components, as shown in Table 1-2. Part 1 is conducted to provide data for PK/PD analyses in diabetic patients with NPDR and to explore the value of different OCT-A assessments as PD marker in DR. Part 2 is the main part of this PoC study and will be conducted in parallel. Both components follow a similar design – except for the randomization ratio and additional examinations in Part 1. Both study subparts will be evaluated together, to the extent that common data are available and at the same time.

Study part	Main purpose	Overall design
Part 1 PK/PD assessment Placebo-controlled, double-ma with 2:1 randomization. Total		Placebo-controlled, double-masked, 2-arm parallel-group design with 2:1 randomization. Total n = 18
		Intra-individual weekly dose escalation in 30-mg increments up to 120 mg once daily.
		Each participant will continue treatment at the individual maximum dose for a total treatment duration of 48 weeks.
Part 2 PoC	Poc Demonstration of PoC based on efficacy outcome after 48 weeks of treatment	Placebo-controlled, double-masked, 2-arm parallel-group design with 1:1 randomization. $n = 40$ per treatment arm
		Intra-individual weekly dose escalation in 30-mg increments up to 120 mg once daily.
		Each participant will continue treatment at the individual maximum dose for a total treatment duration of 48 weeks.

 Table 1-2: Overall study plan

In Part 1, the randomized participants will be titrated at weekly visits in 30-mg increments to the target dose of 120 mg QD, or the maximum individually tolerated dose. After the titration period, the individually reached highest dose will be maintained until the EoT, for the total treatment duration of 48 weeks, followed by a 4-week safety follow-up period. A total of 18 participants are planned to be randomized into Part 1 (12 active; 6 placebo). A schematic study design for Part 1 is provided in Figure 1-1.

In Part 1, additional safety, PK and PD investigations will be performed during the titration phase. On Visits 2 to 6, participants will remain at sites for 4 hours post-dose. During this time, the pulse rate and the blood pressure will be checked, and OCT-A will be used to assess retinal perfusion as PD markers. Blood samples will be drawn for Pop-PK and for PK/PD analyses pre-dose and in two post-dose windows.

Recruitment, screening, and randomization of participants for Part 2 of the study is independent from Part 1. Part 2 of the study is planned to follow the same titration and dosing scheme as Part 1. In Part 2, the participants will be randomized to either placebo (n = 40) or runcaciguat (n = 40). The participants are planned to be titrated at 30-mg increments to the

CONFIDENTIAL
--------------

Page: 12 of 35

maximum tolerated dose or sham titrated. Each participant will continue treatment for a total treatment duration of 48 weeks, followed by a 4-week follow-up period.

Figure 1-1: Schematic study design

To assess the efficacy, the retinal morphology will be investigated by 7-field CFP supported by 7-field FA images for the assessment of the DRSS by a central reading center. Two-step DRSS improvement at 48 weeks of treatment will be the primary efficacy endpoint. Additional DRSS assessments are done after 12 and 24 weeks of treatment. In addition, VTC will be recorded throughout the study and assessed as secondary efficacy endpoint.

During the study, 16 visits are planned, including the screening visit (Visit 1) and the end-ofstudy visit (Visit 16). For the SoA refer to Section 1.3 of the clinical study protocol.

Participants are randomly assigned to one of two study arms. Randomization will be done stratified by baseline DRSS (47 or 53). A combined total of approximately 98 participants for Part 1 and 2 will be randomly assigned for an estimated total of  $\geq$  40 participants per intervention group evaluable for primary endpoint assessment.

During the initial 4 weeks, treatment will be titrated to the target dose of 120 mg runcaciguat or matching placebo. Treatment will continue at the highest tolerated dose until completion of 48 weeks of treatment if tolerated, or until development of a VTC or development of PDR.

An EoS visit will be performed 4 weeks after EoT. This includes both participants who complete the planned treatment period, and participants who discontinue treatment early including treatment discontinuation due to VTC.

The study population is characterized by the following main inclusion criteria:

- Age  $\geq 18$  years
- Moderately severe to severe NPDR in the study eye: DRSS levels 47 or 53
- Diabetes type 1 or 2

- BCVA ETDRS letter score in the study eye of  $\geq$  69 letters (approximate Snellen equivalent of 20/40 or better)
- Refraction with a spherical equivalent from -6 dpt to +5 dpt

## 2. Statistical Hypotheses

The primary endpoint is the proportion of patients with " $\geq$  2-step improvement in DRSS at 48 weeks of treatment in the study eye". This proportion will be denoted as  $\pi_{ACT}$  within the runcaciguat treatment arm and as  $\pi_{PLC}$  within the placebo treatment arm.

The study will be evaluated using a Bayesian approach with non-informative prior distribution. Using this approach for inference it is possible to base decisions directly on the posterior probabilities of the hypotheses of interest. Therefore, in a Bayesian setting it is not necessary to specify an alternative hypothesis.

The hypotheses of interest are the following:

- Hypothesis of clinical activity:  $\pi_{ACT} > \pi_{PLC}$
- Hypothesis of clinical relevance:  $\pi_{ACT} > 0.25$

